26.4.4 Tumour Assessment

Initial disease assessments include:

- Staging by Ann Arbor classification ([Cheson et al 2014](#): see [Table 35](#)).
- Physical exam: attention to node-bearing areas, including Waldeyer's ring, and to size of liver and spleen.
- Complete blood count, platelets, differential, chemistry profile, lactate dehydrogenase
- Whole-body fluorodeoxyglucose (FDG)-positron-emission tomography (PET)/computed tomography (CT) scan.
- Brain imaging (MRI with contrast preferred). MRI of the brain will be performed at Screening only if there is a prior history of CNS involvement or if there are neurologic signs or symptoms present.
- Bone marrow biopsy and aspirate (Section [26.4.1](#)).

DLBCL response criteria: Lugano Response Criteria for Non-Hodgkin's Lymphoma ([Cheson et al 2014](#), see [Table 36](#)).

Baseline tumour assessments will be performed using radiologic imaging by CT with contrast and PET-CT covering neck, chest, abdomen, and pelvis within 30 days before the first dose of AZD4573 ([Table 37](#)). For participants with baseline hepatosplenomegaly, the cranial-caudal measurement of the spleen and longest diameter of the liver will be assessed at screening and all subsequent response evaluations. Unscheduled radiologic scans may be performed at investigator discretion if deemed clinically indicated. Magnetic resonance imaging may be used for imaging assessments if a contrast CT scan is contraindicated or unobtainable. In cases where MRI is desirable, the MRI must be obtained at baseline and at all subsequent response evaluations.

Tumour assessments will be made for measurable disease, non-measurable disease, and new lesions on CT and combined with visual assessment of PET-CT for response assessment according to the revised response criteria for malignant lymphoma ([Cheson et al 2014](#)). See [Table 36](#).

All response assessments will be made by the Investigator. All images for the assessment of response will be collected and stored for central review. Additional disease assessments may be performed as clinically indicated.

CT scans

Bi-dimensional measurements will be recorded for lymph nodes ≥ 1.5 cm in longest diameter in the eCRF. Up to a maximum of 6 dominant, measurable lymph nodal lesions should be

assessed as target lesions. These nodes or masses should be selected according to all of the following:

- They should be clearly measurable in at least two perpendicular dimensions.
- If possible, they should be from disparate regions of the body.
- They should include mediastinal and retroperitoneal areas of disease whenever these sites are involved.

The perpendicular long and short axis diameters will be measured and recorded in the transverse plane at baseline and follow-up. When appropriate, measurable extranodal disease, defined as extranodal lesions (eg, hepatic nodules) with the longest diameter ≥ 1.0 cm, may be included in the 6 representative, measured lesions.

For the selected target lymph nodal lesions, the sum of the product of the perpendicular diameters will be calculated with the percentage change from baseline for assessment of response and nadir for assessment of progression.

All other lesions (including nodal, extranodal, and assessable disease) should be followed as nonmeasured disease (eg, cutaneous, gastrointestinal, bone, spleen, liver, kidneys, pleural or pericardial effusions, ascites) and should be factored into overall response assessment.

Visual interpretation of PET-CT scans

The International Working Group criteria for reviewing PET scans were based on visual interpretation, using mediastinal blood pool as the comparator. The current recommendation is to use the 5-point scale ([Cheson et al 2014](#)).

Assessment of non-measurable lesions

An overall assessment for all other non-target lesions of present, absent, or present with progression will be recorded and factored into response assessment.

Assessment of new lesions

Appearance of any new lesions more than 1.5 cm in any axis during or at the end of therapy, even if all other lesions are decreasing should be considered progression.

Increased FDG uptake in a previously unaffected site should only be considered progression after confirmation with other modalities (eg, CT, MRI, or X-ray).

In participants with no history of pulmonary lymphoma, new nodules identified by CT are benign and should be considered negative for lymphoma. These lesions typically represent

infectious or inflammatory lesions; therefore, if FDG positive, should not be considered positive for lymphoma in the absence of confirmatory tests, (eg, histology).

The presence or absence of new lesions will be recorded in the eCRF.

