Lymph nodes and extralymphatic sites	Score 4 or 5 ^b with reduced uptake compared with baseline and residual mass(es) of any size	$\geq 50\%$ decrease in SPD of up to 6 target measurable nodes and extranodal sites
	At interim, these findings suggest responding disease	When a lesion is too small to measure on CT, assign 5 mm \times 5 mm as the default valve
	At end of treatment, these findings indicate residual disease	When no longer visible 0 \times 0 mm For a node > 5 mm \times 5 mm, but smaller than normal, use actual measurement for calculation
Nonmeasured lesions	Not applicable	Absent/normal, regressed, but no increase
Organ enlargement	Not applicable	Spleen must have regressed by $> 50\%$ in length beyond normal
New lesions	None	None

Response and Site	PET-CT-Based Response	CT-Based Response
Bone marrow	Residual uptake higher than uptake in normal marrow but reduced compared with baseline (diffuse uptake compatible with reactive changes from chemotherapy allowed). If there are persistent focal changes in the marrow in the context of a nodal response, consideration should be given to further evaluation with MRI or biopsy or an interval scan	Not applicable
No response or stable disease:	No metabolic response:	Stable disease:
Target nodes/nodal masses, extranodal lesions	Score 4 or 5 with no significant change in FDG uptake from baseline at interim or end of treatment	< 50% decrease from baseline in SPD of up to 6 dominant, measurable nodes and extranodal sites; no criteria for progressive disease are met
Nonmeasured lesions	Not applicable	No increase consistent with progression
Organ enlargement	Not applicable	No increase consistent with progression
New lesions	None	None
Bone marrow	No change from baseline	Not applicable
Progressive disease:	Progressive metabolic disease:	Progressive disease requires at least 1 of the following PPD progression:
Individual target nodes/nodal masses	Score 4 or 5 with an increase in intensity of uptake from baseline and/or	An individual node/lesion must be abnormal with: LDi > 1.5 cm and Increase by $\geq 50\%$ from PPD nadir and An increase in LDi or SDi from nadir 0.5 cm for lesions ≤ 2 cm 1.0 cm for lesions > 2 cm

Response and Site	PET-CT-Based Response	CT-Based Response

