Extranodal lesions	New FDG-avid foci consistent with lymphoma at interim or end-of-treatment assessment	In the setting of splenomegaly, the splenic length must increase by > 50% of the extent of its prior increase beyond baseline (eg, a 15 cm spleen must increase to > 16 cm). If no prior splenomegaly, must increase by at least 2 cm from baseline New or recurrent splenomegaly
Nonmeasured lesions	None	New or clear progression of pre-existing nonmeasured lesions
New lesions	New FDG-avid foci consistent with lymphoma rather than another aetiology (eg, infection, inflammation). If uncertain regarding aetiology of new lesions, biopsy or interval scan may be considered	Regrowth of previously resolved lesions A new node > 1.5 cm in any axis A new extranodal site > 1.0 cm in any axis; if < 1.0 cm in any axis, its presence must be unequivocal and must be attributable to lymphoma Assessable disease of any size unequivocally attributable to lymphoma
Bone marrow	New or recurrent FDG-avid foci	New or recurrent involvement

^a The Lugano 2014 criteria are used in this study for disease assessment. In line with these criteria, it should be clarified that the study definition of CMR is a Deauville score 1-3.

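### Module 2: Section 26.4.4 contradicts Table 36 on new FDG uptake and new lung nodules, so the same scan can be progressive disease or not

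*Protocol*

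**What the plan says.** Table 36 in Protocol Section 26.4.1 holds the Lugano criteria. Section 27.4.5 sends the efficacy analysis to Section 26.4.1, and Section 27.4.5.4 has investigators determine progression by Lugano 2014. Section 26.4.4 also says that response follows these criteria and refers to Table 36, but then gives rules of its own.

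- **FDG uptake.** Section 26.4.4: "Increased FDG uptake in a previously unaffected site should only be considered progression after confirmation with other modalities", with CT, MRI or X-ray as examples. Table 36, PET-CT column, lists as progression "New FDG-avid foci consistent with lymphoma rather than another aetiology"; biopsy or an interval scan is optional, and only where the cause is uncertain.
- **Nodules.** Section 26.4.4, for participants with no history of pulmonary lymphoma: "new nodules identified by CT are benign and should be considered negative for lymphoma". No size limit is given. Confirmatory tests are mentioned only for FDG-positive lesions. Table 36 has no such exception.
- **New-lesion size.** Section 26.4.4 treats "Appearance of any new lesions more than 1.5 cm in any axis during or at the end of therapy" as progression, whatever the other lesions do. Table 36 uses more than 1.5 cm for a new node but has a separate extranodal rule: "A new extranodal site > 1.0 cm in any axis; if < 1.0 cm in any axis, its presence must be unequivocal" and attributable to lymphoma.
- **Target-lesion growth.** Section 26.4.4 has the SPD calculated with "percentage change from baseline for assessment of response and nadir for assessment of progression". Table 36 judges progression lesion by lesion ("An individual node/lesion must be abnormal with" a longest diameter above 1.5 cm, a PPD at least 50% above nadir, and a minimum gain in diameter) and uses SPD for partial response and stable disease.

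The text shown contains no sentence saying which of the two prevails.

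**The concern.** A site that follows the detailed instructions in Section 26.4.4 and a site that reads Table 36 can classify the same images differently. In Module 2 the PD call does a lot of work. It is the event for PFS and DoR, and it closes the window in which a response counts towards ORR (Section 27.4.5.1). It feeds the 75% data cut-off trigger (Section 22.1). It also starts combination treatment (Section 24.4, Table 29). At the first decision point in Table 29, stable disease continues monotherapy unless the investigator chooses otherwise, while PD starts Period 2, so a PD/not-PD disagreement there can change which treatment is given.

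**Working it through.** The protocol states no figure to reproduce. The check is to put both texts to the same scan. Lesion sizes below are assumptions chosen for illustration.

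**Direct contradictions**

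1. New FDG-avid focus consistent with lymphoma, no correlate on CT, MRI or X-ray. Table 36: PD. Section 26.4.4: not PD, because its wording is exclusive (only after confirmation).
2. New 2.0 cm lung nodule on CT, no history of pulmonary lymphoma. Table 36: PD, since 2.0 cm exceeds the 1.0 cm extranodal limit. Section 26.4.4, nodule sentence: negative for lymphoma. Section 26.4.4, 1.5 cm sentence: PD. The section therefore also disagrees with itself.

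**Lesser mismatches**

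3. New 1.2 cm liver lesion. Table 36: PD. Section 26.4.4: does not reach the only size it names, but the section does not say that smaller lesions are not PD.
4. SPD against individual PPD:
   - Six nodes of 2.0 × 2.0 cm, SPD 6 × 4 = 24 cm². One grows to 2.6 × 2.4 cm. PPD: 6.24/4 − 1 = +56%; longest diameter +0.6 cm, against 0.5 cm required for lesions up to 2 cm. PD by Table 36. SPD: (5 × 4 + 6.24)/24 − 1 = +9.3%.
   - One node goes from 3.0 × 2.0 to 4.0 × 3.0 cm while five shrink from 2.0 × 2.0 to 1.5 × 1.5 cm. PPD: 12/6 − 1 = +100%; longest diameter +1.0 cm. PD by Table 36. SPD: (12 + 5 × 2.25)/(6 + 5 × 4) − 1 = 23.25/26 − 1 = −10.6%.
   - Six nodes go from 1.9 × 1.6 to 2.3 × 2.0 cm. SPD: 4.60/3.04 − 1 = +51.3%, yet each diameter gains only 0.4 cm. Not PD by Table 36.

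   The two measures can diverge in either direction. Section 26.4.4 attaches no threshold to the SPD change, so these examples show a mismatch of measure, not a second verdict.

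**Where the rules bite.** In Table 37 the scheduled 8-week scan in Period 1 is contrast CT without PET, so the CT rules, including the nodule sentence, apply at the first switch decision. Scheduled PET, and with it the FDG rule, enters at 17 weeks.

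**Size.** With about 12 participants (Section 27.2), one reclassified participant is 1/12 = 8.3 percentage points in a rate over all participants, and the 75% trigger is 0.75 × 12 = 9 participants. Scheduled scans are 9 weeks apart up to week 26 and 12 weeks apart afterwards, so a PD call that did slip to the next scheduled scan would move that participant's progression date by 9 to 12 weeks.

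**The case against.** The protocol names Lugano 2014 as the standard in several places, and Section 26.4.4 itself refers to Table 36, so it can be read as a supplement to that table. That reading disposes of some stronger inferences a reader might draw:

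- That a new 1.2 cm extranodal lesion is not PD under Section 26.4.4. The 1.5 cm sentence states a sufficient condition; it does not exclude smaller lesions.
- That SPD from nadir is a rival progression rule. It has no threshold and is nowhere said to decide PD.
- That extranodal disease is left out of the measured lesions. The same section lets measurable extranodal lesions be among the six.
- That Section 26.4.4 calls PD later in general. This is not shown: the third SPD example would point the other way if SPD were a rule, and the 1.5 cm sentence does not require attribution to lymphoma.

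The supplement reading does not rescue the FDG and nodule sentences, because each withholds a PD call that Table 36 makes. The nodule sentence could be taken as a specific exception to the 1.5 cm sentence, but the text does not say so.

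The practical reach is limited. Every scheduled PET in Tables 37 and 38 is paired with a contrast CT, so a second modality is usually at hand at the same visit and a delay is not automatic. Efficacy in Module 2 Part A is exploratory, no hypothesis is tested, and the primary endpoints are safety. The 75% trigger is capped by the alternative of about 6 months after the last participant's first dose. Section 18.5 also records a decision to halt enrolment permanently.

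**Conclusion.** The point holds at moderate severity. Section 26.4.4 contradicts Table 36 on unconfirmed FDG-avid foci and on new CT nodules without a pulmonary history, and the nodule sentence contradicts the 1.5 cm sentence beside it. The size and SPD wording are secondary mismatches that should be tidied at the same time.

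The consequence is ambiguity in exploratory PFS, DoR and ORR, in the cut-off trigger and in the Period 1 to Period 2 switch. Each affected participant is worth 8.3 points at n = 12. The documents give no basis for estimating how many would be affected, so no overall bias or direction is claimed.

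This assumes that the nodule sentence means lung nodules, as its context suggests, and that no precedence rule stands in a part of the protocol not shown. A reader might infer the same fault in Module 1. The corresponding Module 1 section is not in the text shown, so nothing can be asserted about it.

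**What to change.** Reconcile the FDG, nodule and 1.5 cm sentences under the new-lesions heading of Section 26.4.4, and its SPD sentence, with Table 36, so that one progression rule set applies. Add one sentence stating which text prevails for investigator-called PD and for the efficacy endpoints, and apply it consistently to all reads. Because PD governs treatment in this module, which rule to keep is for the sponsor and its clinical advisers to decide; this review does not choose.

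The cost is protocol wording and a note to sites. No new scans are needed. Images are already collected and stored for central review, so any past call that turned on these sentences can be re-read under the reconciled rule.

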26.5 Human Biological Samples

Please refer to Section [8.5](#) for general information on collection and handling of al samples.

26.6 Pharmacokinetics

Venous blood samples for determination of concentrations of AZD4573 in plasma will be taken at the times presented below.

Samples for PK should be collected from the arm that is not used for the infusion where possible. If this is not possible, then separate lines should be used for drug infusion and sampling. If there is no other option than to use a central line (PICC-line) for drug administration/sample collection, it is mandatory this is a multi-lumen line. This information should be recorded where possible. AZD4573 should be administered using a different lumen from the one which is used for sample collection. The sample collection lumen needs to be flushed twice prior to collecting the sample. AZD4573 administration needs to be paused during the time the samples are collected to prevent sample contamination.

Sample collection date, time, and exact dosing will be recorded for both AZD4573 and acalabrutinib. Samples will be collected, labelled, stored, and shipped as detailed in the Laboratory Manual.

On the day of PK collection, acalabrutinib capsules should be brought to site by the participant and taken within 5 minutes before initiation of AZD4573. The actual date and time of AZD4573 and acalabrutinib dosing will be recorded.

If the participant, in error, takes acalabrutinib at home before coming to the site on the day of PK collection, PK sampling should be conducted at the timepoints listed according to AZD4573 dose provided that the exact time of acalabrutinib dosing was recorded. If there is no record for acalabrutinib dosing, PK should not be collected.

Part A – Period 1

Plasma samples for PK analysis will be taken at the following time points:

- Cycle 1, Weeks 1 through 3 and Cycle 2, Day 1:
 - Predose (within 2 hours prior to AZD4573 administration)
 - 1 hour (\pm 15 minutes) after the start of infusion

- 2 hours (\pm 15 minutes) after the start of infusion
- 4 hours (\pm 30 minutes) after the start of infusion
- 7 hours (\pm 1 hour) after the start of infusion, and
- 24 hours (\pm 1 hour) after the start of the infusion.

The timing and frequency of the PK samples may be adjusted during the study, dependent on emerging data, to ensure appropriate characterisation of the plasma concentration-time profiles.

Part A – Period 2

Plasma samples for PK analysis will be taken at the following time points:

- Cycle 1, Weeks 1 and 3:
 - Predose (within 2 hours prior to AZD4573 [and acalabrutinib during Period 2] administration)
 - 1 hour (\pm 15 minutes) after the start of infusion
 - 2 hours (\pm 15 minutes) after the start of infusion
 - 4 hours (\pm 30 minutes) after the start of infusion
 - 7 hours (\pm 1 hour) after the start of infusion, and
 - 24 hours (\pm 1 hour) after the start of the infusion (and prior to acalabrutinib dosing in Period 2).

The timing and frequency of the PK samples may be adjusted during the study, dependent on emerging data, to ensure appropriate characterisation of the plasma concentration-time profiles.

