cc Exploratory blood **CCI** [REDACTED] Whole blood samples will be collected at Screening and Cycle 1 Weeks 1-3 at predose (within 2 h prior to dosing), 2 h (\pm 15 mins) and 24 h (\pm 2 h) after the start of the infusion and on Day 1 of Cycles 2, 3, 5, and 7 predose (within 2 h prior to dosing), and at every scheduled or unscheduled tumour assessment scan (if on the day of infusion, collect pre-infusion), and at disease progression/end of treatment. If a sample is not taken at End of Treatment, a sample should be obtained at the 30-day SFU.

dd **CCI** sample for **CCI** [REDACTED] isolation will be collected at Cycle 1, Week 1 predose.

ee An optional saliva sample for genomics initiative research will be taken from consenting participants prior to the first dose of IP. If for any reason the sample is not taken before dosing it may be taken at any visit until the last study visit. Only one sample should be collected per participant for genetics during the study.

ff A biopsy will be taken at disease progression for participants who consent. The disease progression sample may be taken at the SFU visit if not collected previously.

gg Bone marrow biopsy and aspirate: **CCI** [REDACTED]

hh See [Table 37](#) for schedule of disease assessments, including mandatory PET assessments. Disease assessments will be done by the Investigator using the Lugano Response Criteria for Non-Hodgkin's Lymphoma ([Cheson et al 2014](#)). Additional disease assessments may be performed as clinically indicated.

ii AZD4573 is to be administered as an absolute (flat) dose, 2-h (\pm 15 mins) IV infusion on a once-weekly schedule.

jj If a participant is attending Cycle 9+ visits according to a modified schedule, in which AZD4573 is not infused and assessments are not performed every week, the Day 1 assessments should be performed at least once per cycle.

kk The End of Treatment visit is the last visit attended by the participant prior to the 30-Day SFU on the study. At this visit, the participant does not receive IMP and should undergo the applicable assessments associated with the Cycle and visit they have reached, plus those shown in the "Disease Assessment/End of Treatment" column of the SoA.

ll AZD4573 should be administered at least 5 days apart

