24.1 Study Intervention(s) Administered

24.1.1 Investigational Products

AZD4573 will be administered as an absolute (flat) dose, 2-hour (\pm 15 minutes) IV infusion once weekly, at least 5 days apart, alone and in combination with acalabrutinib 100 mg twice daily continuously.

AZD4573 and acalabrutinib will be supplied by AstraZeneca. CC1

Detailed

information on the drug products and administration guidelines are in the AZD4573 Handling Instructions and acalabrutinib participant leaflet.

Table 28 Investigational Products

Intervention Name	AZD4573	Acalabrutinib
Type	Drug	Drug
Dose Formulation	Concentrate for solution for infusion	Capsules
Unit Dose Strength(s)	1.5 mg/mL	100 mg
Dose	Part A Period 1: 12 mg* Part A Period 2: dose to be established based on emerging data from Module 1	100 mg BID
Route of Administration	IV infusion	Oral
Use	Experimental	Experimental
IMP and NIMP	IMP	IMP

Intervention Name	AZD4573	Acalabrutinib
Sourcing	Provided centrally by AstraZeneca	Provided centrally by AstraZeneca
Packaging and Labelling	Study Intervention will be provided in vials. Each vial will be labelled as required per country requirement	Study Intervention will be provided in bottles. Each bottle will be labelled as required per country requirement
Current/Former Name(s) or Alias(es)	AZD4573/ AZ13810325	Acalabrutinib/ACP-196 /Calquence

*In Period 1, target dose of 12 mg achieved through intra-patient ramp up from starting dose on Day 1 (6 mg), with subsequent titration to the intermediate dose on Day 8 (9 mg), and to target dose of 12 mg on Day 15.

Abbreviations: BID = twice daily; IMP = investigational medicinal product; IV = intravenous;
NIMP = non-investigational medicinal product.

Labels will be prepared in accordance with Good Manufacturing Practice and local regulatory guidelines and will be translated into the local language. The labels will fulfil Good Manufacturing Practice Annex 13 requirements for labelling.

All IPs should be kept in a secure place under appropriate storage conditions. The IP label on the vial (AZD4573) or bottle (acalabrutinib) specifies the appropriate storage conditions.

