26.1.4 Electrocardiograms (ECGs)

ECG will be performed at timepoints specified in the SoA (Section [19.2](#)).

Twelve-lead ECGs will be obtained after the participant has been resting semi-supine for at least 10 minutes before the times indicated. All ECGs should be recorded with the participant in the same physical position where possible.

If an abnormal ECG finding at Screening or baseline is considered to be clinically significant by the Investigator, it should be reported as a concurrent condition. If a clinically significant abnormal ECG finding occurs on study, contact the Medical Monitor.

Single ECGs will be collected for local and central analysis at the following timepoints:

- Screening

Period 1 and Period 2

- Cycle 1, Weeks 1 through 5, and Cycle 2, Day 1:
 - Predose (at the day of infusion prior to infusion)
 - End of infusion (within 30 minutes of end of infusion)
- Cycles 3+ Day 1 of each cycle:
 - Within 30 minutes after the end of infusion
- 30-Day SFU

Any abnormal finding in the ECG tracing will be evaluated by the Investigator and will be specifically documented and registered in the eCRF. Throughout the study, clinically relevant new findings or worsening of a pre-existing finding in the ECGs (parameters or abnormal findings in the tracing) must be considered an AE and must be recorded in the AE CRF form.

If an unscheduled ECG is done at any time, then an electrolyte panel (ie, calcium, magnesium, potassium), and troponin I/troponin T must be done to coincide with the ECG testing. Note: either a troponin I or troponin T assay can be used per SoC at the respective hospital. If the hospital has both a SoC troponin I and troponin T assay available, the investigator shall use only one consistently for the duration of the study.

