27.4.6 Pharmacokinetics

Pharmacokinetic results are a secondary objective for Part A.

Plasma concentrations of AZD4573 plus acalabrutinib and its metabolite ACP-5862 will be summarised by nominal sample time. Plasma concentrations and derived PK parameters will be summarised by treatment period. Plasma concentrations and the derived PK parameters at each time point will be summarised according to treatment by the following summary statistics:

- The geometric mean (gmean)
- Coefficient of variation (CV)
- Gmean \pm standard deviation
- Arithmetic mean calculated using untransformed data
- Standard deviation calculated using untransformed data
- Minimum
- Median
- Maximum
- Number of observations

The PK data for AZD4573, acalabrutinib and its metabolite ACP-5862 will also be displayed graphically. Displays will include plasma concentration participant profiles (on the linear and log-scale) versus time and gmean concentration (\pm standard deviation) versus time, stratified by dose.

Scatter plots of PK parameters versus dose, or log-dose, will also be considered to assess dose proportionality.

Derived PK parameters to be determined include Cmax, AUC0-t, AUClast, AUC0-inf, tmax, and t1/2.

Additional PK parameters may be determined.

27.5 Safety Review Committee – Module 2

An SRC, which includes the principal investigators, is tasked with the review of the available safety data (AEs and available pharmacokinetics/pharmacodynamics [PKPD]

data) for AZD4573 alone or in combination with acalabrutinib. All decisions made by the SRC will be documented in writing in the form of meeting minutes.

The SRC will meet during Module 2, Part A after the first 6 participants have completed Period 1, Cycle 1, and again after the first 6 participants entering Period 2 have completed Cycle 1. The AZD4573 monotherapy RP2D established in DLBCL (12 mg once weekly; study D8230C00001) will be evaluated in MCL participants (Period 1), and safety and tolerability compared with the known safety profile in DLBCL participants to confirm the RP2D in the MCL population. The AZD4573 + acalabrutinib combination RP2D established in participants with DLBCL from Module 1 will be evaluated in MCL participants (Period 2) after receiving AZD4573 monotherapy RP2D in Period 1.

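### The only AZD4573 PK draw near the peak is timed from the start, not the end, of a variable-length infusion, so observed Cmax in Module 2 reads modestly low and noisier than it need be

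*Protocol*

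**What the plan says.** Section 24.1.1 sets the infusion: "AZD4573 will be administered as an absolute (flat) dose, 2-hour (\pm 15 minutes) IV infusion once weekly". Footnote ii of the Period 1 schedule (Table 23) says the same: "AZD4573 is to be administered as an absolute (flat) dose, 2-h (\pm 15 mins) IV infusion on a once-weekly schedule", and so does footnote ee of Table 24 for Period 2.

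Section 26.6 counts every PK draw from the start of infusion, with the same list of times in both periods. The draw nearest the end is set at "2 hours (\pm 15 minutes) after the start of infusion". The one before it is at 1 h with an equal tolerance, and the one following is at 4 h with 30 min either way. The rest are predose, 7 h and 24 h. Table 23 footnote u and Table 24 footnote q repeat these times. No PK draw is tied to the end of infusion.

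Other measurements are tied to it. Section 26.1.3 takes blood pressure and pulse at the end of infusion, up to 10 minutes after the dose. Section 26.1.4 takes ECGs at "End of infusion (within 30 minutes of end of infusion").

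Section 26.6 also says that "AZD4573 administration needs to be paused during the time the samples are collected to prevent sample contamination". The sentence follows the central-line instructions, and it is not clear whether it applies to every participant. The same section has actual sample and dosing times recorded and allows sampling times to be adjusted on emerging data.

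Section 27.4.6 summarises concentrations by nominal time and states: "Derived PK parameters to be determined include Cmax, AUC0-t, AUClast, AUC0-inf, tmax, and t1/2". Table 26 makes plasma PK, alone and with acalabrutinib, the secondary objective of Part A.

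**The concern.** During a constant-rate infusion the concentration rises until the infusion stops and then falls. The true Cmax is therefore at the end of infusion, and a draw on either side of it reads at or below the peak. The error goes one way only and does not average out.

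The end of infusion and the 2 h draw each have their own 15 min tolerance, and nothing makes them move together. The neighbouring draws are at 1 h, while the drug is still running in, and at 4 h, so nothing is scheduled between 2 h 15 and 3 h 30. If the 2 h draw misses the peak, no other draw is placed to catch it. Recording the actual time shows by how much it was missed but does not supply the missing concentration. Because concentrations are summarised by nominal time, the 2 h row also mixes samples taken during infusion with samples taken after it.

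At stake is an avoidable, one-sided error in a named PK parameter, in a module of about 12 participants (Section 27.2).

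**Working it through.** The plan gives no figure of its own to reproduce on this point.

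**Inputs from the protocol.** Infusion length T: 1.75 to 2.25 h. Draws from start: 0.75 to 1.25 h, 1.75 to 2.25 h, 3.5 to 4.5 h.

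**Assumptions (not in the document).** One compartment; half-life 0.5, 1, 2, 4 or 8 h; T and each draw time independent and uniform within their windows.

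**Step 1, timing.** Offset = draw time minus T.
- Earliest: 1.75 - 2.25 = -0.50 h, or 30 min before the end.
- Latest: 2.25 - 1.75 = +0.50 h, or 30 min after the end.
- With uniform windows, about half the draws fall before the end and the mean absolute offset is 10 min.

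**Step 2, the 2 h draw alone at its extremes.** With k = ln 2 / half-life:
- 30 min late: observed/true = exp(-0.5k)
- 30 min early: observed/true = (1 - exp(-1.75k)) / (1 - exp(-2.25k))

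For a 1 h half-life, k = 0.693. Late: exp(-0.347) = 0.71. Early: (1 - 0.297) / (1 - 0.210) = 0.703 / 0.790 = 0.89.

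**Step 3, let the other draws count.** Observed Cmax is the highest concentration over all draws. At a 0.5 h half-life (k = 1.386), a draw 30 min late reads 0.50. But a 1 h draw taken as early as 0.75 h in the same 1.75 h infusion already reads (1 - exp(-1.040)) / (1 - exp(-2.426)) = 0.646 / 0.912 = 0.71, so observed Cmax cannot be 0.50. Searching all compliant combinations gives a worst value of 0.69 at that half-life.

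**Step 4, simulation** (1,000,000 profiles, Cmax = maximum of the 1, 2 and 4 h draws):

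| Half-life (h) | 2 h draw 30 min late | 2 h draw 30 min early | Worst compliant Cmax | Mean bias | Added CV | More than 10% low |
|---|---|---|---|---|---|---|
| 0.5 | 0.50 | 0.95 | 0.69 | -8% | 9% | 36% |
| 1 | 0.71 | 0.89 | 0.71 | -7% | 7% | 25% |
| 2 | 0.84 | 0.84 | 0.84 | -6% | 4% | 16% |
| 4 | 0.92 | 0.81 | 0.81 | -5% | 4% | 12% |
| 8 | 0.96 | 0.79 | 0.82 | -4% | 5% | 15% |

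The second and third columns are the 2 h draw on its own. The rest use the highest of the three draws.

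**Step 5, after the fix.** A draw within 5 min before the end of infusion gives a mean observed/true Cmax of 0.98 to 1.00 and a worst case of 0.96 over the same half-lives. A draw 0 to 5 min after the end is less robust: at a 0.5 h half-life its mean is 0.94 and its worst case 0.89.

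**The case against.** The strongest reply is that the effect is modest and the start-based clock has a reason. In Period 2 the same samples measure acalabrutinib and its metabolite, and acalabrutinib is taken within 5 minutes before the infusion begins, so the start of infusion is the natural common clock. The 2 h pharmacodynamic and exploratory draws (Sections 26.7.1 and 26.9.6) use it too. This stands as a condition on the remedy but not as a reason to leave the PK draw unanchored. A draw within 5 min before the end falls between 1 h 40 and 2 h 15 from start, almost wholly inside the present window, and the matched draws can move with it.

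A reader might infer more than the documents support in four ways:
- **A biased comparison of AZD4573 alone with the combination.** Infusion length and draw windows are the same in both periods, so with similar timing habits much of the bias cancels and mainly noise remains. Even if the half-life went from 0.5 to 8 h between periods, the ratio would shift by only about 4% (0.958 / 0.923 = 1.04).
- **A distorted AUC.** Actual times are recorded, and AUC can be computed on them.
- **A spoiled Cmax-ECG relation.** No such analysis is specified. Section 27.4.4 only allows plots of safety parameters against concentration, and the ECG window of 30 min is no tighter than the worst PK offset.
- **A pause that pushes the gap beyond 30 min.** If the 2 h (±15 min) limit includes pauses, it cannot. The protocol does not say whether it does.

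It is also fair that sampling times may be adjusted on emerging data, and that Section 18.5, in the Module 1 part but worded for the study, reports enrolment permanently halted. Few future samples may be affected.

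**Conclusion.** The point holds as a modest weakness. The timing arithmetic is exact: a compliant draw can be 30 min either side of the end of infusion. The direction is also certain for a constant-rate infusion, since observed Cmax is never above the true peak.

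The size rests on assumptions about half-life, compartment structure and the use of the windows. Over half-lives of 0.5 to 8 h, mean bias is about -8% to -4%, added CV about 9% to 4%, 12% to 36% of profiles read more than 10% low, and the worst compliant case is about 0.7 to 0.84 of the true peak. A reader who looks at the 2 h draw alone might conclude that Cmax can read at half the true value. That does not follow, because the 1 h draw sets a floor at short half-lives.

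The effect is mainly noise plus a small downward bias in a secondary, descriptive parameter. No hypothesis is tested and the primary safety objective is not touched. The change is worth making because it is cheap.

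**What to change.** In Section 26.6 (both periods), Table 23 footnote u and Table 24 footnote q, define the 2 h AZD4573 draw as: *end of infusion, within 5 minutes before the infusion is stopped*. Record the actual infusion stop time and any pause. Leave the existing flush and pause instructions in Section 26.6 as they are. Take the matched 2 h pharmacodynamic and exploratory draws at the same moment, so that PK and PD stay paired. Keep all other sampling times.

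For samples already taken, report each Cmax with its actual offset from the end of infusion.

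The cost is wording in Section 26.6, the two footnotes, the sections for the matched draws and the Laboratory Manual. The number of samples stays the same. The downside is a tighter window for site staff.
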